Data Sources: Case Report Forms (CRFs). Collection of data includes but not limited to subject demographics, adverse events, serious adverse events and concomitant medications. The following questionnaires will be utilized to collect data directly from participating subjects:

- WHODAS 2.0
- WPAI:GH V2.0
- K10
- Flourishing Scale
- Subject Vitality Scale
- Disease-specific PROs that are commonly used in clinical practice (HAQ-DI, SIBDQ, DLQI)

Study Size: It is anticipated that the three groups will respond differently to adalimumab treatment over the study period and there is reason to believe that these groups will be different at baseline. Therefore, the sample size will be powered for rheumatoid arthritis and Crohn's disease. Approximately 80 subjects will be enrolled into each of these 2 parallel study groups allowing for detection of within participant effect sizes of approximately 0.40 as statistically significant (2-tailed $\alpha=0.05$) with 90% power. A minimum of 30 subjects with psoriasis will also be enrolled. A minimum number of 190 patients will be enrolled into the study.

Data Analysis: Primary Endpoint Analysis

Change in total WHODAS 2.0 score at 6 months after the initiation of adalimumab, in those patients continuing on adalimumab (responder population), across all indications. This change will be summarised as the mean and 95% confidence interval and will be tested with a paired t-test.

Secondary Endpoint Analyses

- Change in disease-specific indices (HAQ-DI, SIBDQ, DLQI), WPAI:GH, K10, Flourishing Scale, Subject Vitality Scale at 2, 4 and 6 months after the initiation of adalimumab, in those patients continuing on adalimumab (responder population). These changes will be summarised as the means and 95% confidence intervals and will be tested with paired t-tests.
- Change in total WHODAS 2.0 score at 6 months after the initiation of adalimumab, in those patients continuing on adalimumab (responder population), compared with those patients not continuing on adalimumab (non-responders). The mean changes in these two groups will be compared using an independent t-test.

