9.8 Data Analysis

9.8.1 Definitions

9.8.1.1 Participant Population

All participants who are recruited into the study and start study medication will be used for analysis. A full analysis set will be used for the analysis of the efficacy outcomes with all available data used for the analyses of each outcome at the relevant time points. Efficacy measures are not assessed after a participant discontinues adalimumab. The exception to this will be the analysis of proportion of patients at 6 months who remain on adalimumab, having satisfied the requirements for application for renewal of subsidy by Special Authority. Any participants for whom this assessment is not available will be assumed to have not met these requirements. The primary population for the evaluation of study safety objectives will be the safety population, defined as all participants enrolled into the trial who started study medication. Safety outcomes will only be considered while the patient is on adalimumab. A standard consort diagram describing participant flow (including loss to follow-up and discontinuations for any reason) through the study will be generated.

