9.8.2 Statistical Analyses

The primary analysis of study efficacy measures will be performed using the full analysis set.

Tables showing standard descriptive statistics (including means, standard deviations, standard errors, medians, ranges and frequencies and percentages), graphs, and participant data listings will be used to summarize the baseline demographic and clinical characteristics, and the efficacy and safety data at relevant time-points. Tabular and graphical summaries will represent data separately for each indication group.

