9.8.4 Primary Efficacy Analyses

The primary efficacy outcome is the change in the total WHODAS 2.0 score at 6 months after the initiation of adalimumab, across all indication groups. This change will be summarised as the mean and 95% confidence interval and will be tested with a general linear model which includes participant, indication and baseline WHODAS 2.0 score as terms in the analysis.

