9.8.5 Secondary Efficacy Analyses

The following secondary endpoints will be analysed and summarised using general linear models and paired t-tests. The analyses summarising the changes across all indications will include participant, baseline levels and indication as terms in the analyses. Those analyses analysing changes within indications will use paired t-tests. Mean changes will be summarised with 95% confidence intervals derived from these analyses.

- Change in total WHODAS score 2 and 4 months after the initiation of adalimumab across all indications
- Change in total WHODAS score 6 months after the initiation of adalimumab in each indication
- Changes in WPAI:GI, K10, Flourishing Scale, and Subject Vitality Scale scores at 2, 4 and 6 months after the initiation of adalimumab, across all indications

- Change in disease-specific scores (HAQ-DI, SIBDQ, DLQI) at 2, 4 and 6 months after the initiation of adalimumab, in each indication

The proportion of patients at 6 months who remain on adalimumab, having satisfied the requirements for application for renewal of subsidy by special authority as defined below for each indication will be summarised for all indications combined and separately. These proportions will be summarised with exact 95% confidence intervals.

- **Rheumatoid arthritis:** $\geq 50\%$ decrease in active joint count from baseline AND a clinically significant response to treatment in the opinion of the physician
- **Crohn's disease:** CDAI score reduction by 100 points or CDAI score ≤ 150
- **Psoriasis:** PASI score reduction of $\geq 75\%$; or in the case of a patient had severe chronic plaque psoriasis of the face, or palm of a hand or sole of a foot at the start of treatment, the patient has a reduction in the PASI symptom subscores for all 3 of erythema, thickness and scaling, to slight or better, OR $\geq 75\%$ reduction in affected skin area.

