9.9 Missing Data

Efficacy measures are not assessed after a participant discontinues adalimumab. The exception to this will be the analysis of proportion of patients at 6 months who remain on adalimumab, having satisfied the requirements for application for renewal of subsidy by special authority. Any participants for whom this assessment is not available will be assumed to have not met these requirements. There will be no other imputation for missing data.

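### The primary test in 9.8.4 includes a participant term although each person gives one change score: if fixed it leaves no residual degrees of freedom, if random it is redundant, and the Abstract names a different test and population

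*Combined protocol and SAP*

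**What the plan says.** Section 9.8.4 defines the primary outcome as the change in total WHODAS 2.0 score at 6 months across indications. The change is to be summarised by its mean and 95% confidence interval and "tested with a general linear model which includes participant, indication and baseline WHODAS 2.0 score as terms in the analysis". The section does not say whether participant is fixed or random, gives no visit term, and describes no layout with more than one row per person.

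Section 9.8.5 carries the same terms to the secondary changes across indications, whose models "will include participant, baseline levels and indication as terms in the analyses". It adds: "Mean changes will be summarised with 95% confidence intervals derived from these analyses". Changes within an indication use paired t-tests, and proportions use exact intervals.

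The Abstract describes the same primary endpoint differently: "This change will be summarised as the mean and 95% confidence interval and will be tested with a paired t-test". Its population is "in those patients continuing on adalimumab (responder population), across all indications". Section 9.8.2 says instead: "The primary analysis of study efficacy measures will be performed using the full analysis set".

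Two further rules bear on the population. Section 9.8.1.1 states: "Efficacy measures are not assessed after a participant discontinues adalimumab". Section 9.9, after the rule for the Special Authority renewal proportion, states: "There will be no other imputation for missing data".

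**The concern.** Indication and baseline score do not vary within a person. If each person contributes one change, fixed participant terms already fit every observation exactly, and nothing is left from which to estimate error. The analyst then has to replace the stated model, and the document offers no single replacement because the Abstract and 9.8.4 name different tests in differently labelled populations.

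What is at stake is the standard error and p-value for the primary endpoint, and the intervals for the cross-indication secondary endpoints. The estimated raw mean change is not at stake. Section 9.10 has the interim analysis report the primary and secondary efficacy endpoints, and section 6.0 dates that lock 01 March 2016. If the text is not settled by then, the choice of model would be made with outcome data in hand.

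**Working it through.** **Inputs.** Planned group sizes are 80, 80 and 30, total 190 (9.2, 9.6). Maximum sizes are 100, 100 and 50, total 250 (9.6). Model terms and endpoint lists come from 9.8.4, 9.8.5, 8.0 and 9.1. The plan gives no figure for residual df.

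**The plan's own power figure.** Section 9.6 claims 90% power for a within-participant effect of about 0.40 with about 80 per group, two-sided alpha 0.05. A paired t-test needs 68, and 80 gives 94.2%, so the claim is met with a margin. It concerns the within-indication paired tests, which the participant term does not touch.

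**Residual df, one change per person, participant fixed.** df = rows − rank. The columns are intercept 1, participant 189, indication 2 and baseline 1, total 193. The last three add nothing to the rank.

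| Participants with a month-6 change | Rank | Residual df |
|---|---|---|
| 190 | 190 | 0 |
| 250 | 250 | 0 |
| 133 (assumed 70%: 56/56/21) | 133 | 0 |

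**Participant random, one change per person.** The variance of each change is (participant variance + residual variance). The two parts cannot be separated, but only their sum enters the standard errors of the fixed terms. The fit is therefore that of indication + baseline alone: rank 1 + 2 + 1 = 4, df = 190 − 4 = 186.

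**Layouts that would give the term a role.**
- Baseline and month-6 rows, participant fixed, plus a visit term: 380 rows, rank 191, df 189. This reproduces the paired t-test, and indication and baseline remain aliased with participant.
- The same rows with only the listed terms: rank 190, df 190, but no term represents the change.
- Changes at months 2, 4 and 6 stacked, participant fixed: 570 rows, df 570 − 190 = 380 without visit, or 570 − 192 = 378 with it. With participant random, indication and baseline become estimable.

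Section 9.8.4 states none of these.

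**Secondary analyses affected.** As listed in 9.8.5: WHODAS at months 2 and 4, plus four questionnaires at three times, 2 + 4 × 3 = 14, counting the work-productivity questionnaire as one score. Sections 8.0 and 9.1 place the four questionnaires at month 6 only, giving 2 + 4 × 1 = 6.

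**What the choice of replacement does.** Suppose participant is dropped and the overall mean is read from the indication + baseline model with its ordinary standard error. If baseline explains a share R2 of the variance of the change, that standard error is about sqrt(1 − R2) times the paired t-test's. At assumed R2 of 0.1 and 0.3 the ratios are 0.95 and 0.84. For the population mean change, approximate coverage is 2Φ(1.96 × 0.949) − 1 = 93.7% and 2Φ(1.96 × 0.837) − 1 = 89.9%. Simulation at 80/80/30 (20,000 runs, normal errors, no indication difference) gave 93.6% and 90.1%, against 94.9% and 95.0% for the paired t-test. For the mean at the observed baselines, the same model covered 95.1% and 94.7% (8,000 runs).

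Weighting also matters. In units of the residual SD, the standard error of an equally weighted mean is sqrt((1/80 + 1/80 + 1/30)/9) = 0.081. Weighted by group size it is 1/sqrt(190) = 0.073.

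**Cost of the pooled paired t-test.** If psoriasis differs from the other two groups by d SD, its standard error grows by sqrt(1 + p(1 − p)d²) with p = 30/190 = 0.158. This is 1.011 at an assumed d = 0.4 and 1.042 at d = 0.8.

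**The case against.** The strongest reply is that the plan never calls participant fixed. A reader might infer from the zero df that the primary analysis cannot be computed at all. The documents do not support that. Zero df needs fixed terms and one row per person; under the random reading the term is merely superfluous. The primary mean and interval can also be taken directly from the change scores, and the Abstract already holds a computable test.

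A reader might likewise infer that 14 secondary intervals are impossible. Section 9.8.5 lists several questionnaires at three visits, so a repeated-measures model may have been meant, and such a model is estimable. What stands is that neither a visit term nor the status of participant is given. The count of 14 is also not settled: 9.4 and the Abstract's secondary analyses support later-visit analyses of all the questionnaires, while 8.0 and 9.1 do not.

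A third tempting inference is that dropping participant always yields intervals that are too narrow. That holds only if the target is the population mean with baselines regarded as sampled. For the mean at the observed baselines, coverage is nominal, and 9.8.4 does not say which is wanted.

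It can also be said that choosing the paired t-test over deleting one word is a preference, particularly since 9.6 expects the groups to differ at baseline and in response. That is fair, and both repairs are acceptable.

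Finally, the population mismatch may look harmless because efficacy is not assessed after discontinuation. The Abstract, however, also plans to compare the 6-month WHODAS change between continuers and non-continuers, which needs scores that 9.8.1.1 and 9.9 say are not collected. The documents therefore do not settle how wide the gap is.

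**Conclusion.** The point holds in a limited form. The participant term in 9.8.4 has no valid role with one month-6 change per person: residual df is 0 at any sample size if it is fixed, and it is redundant if it is random. The same terms underlie the intervals of 14 cross-indication secondary analyses under 9.8.5, or 6 under 8.0 and 9.1. This rests on reading the response as 9.8.4 defines it; a multi-visit layout would change the result but has to be written down.

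Separately, two current sections give different primary tests and populations for one endpoint. That contradiction stands however the participant term is read.

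Power is not the problem. The paired t-test detects 0.236 SD with 90% power at 190, and still has about 99% power at 0.40 SD with an assumed 114 participants (60%). The interim results are not to influence conduct (9.10), so the reason for acting before that lock is to fix the analysis before outcome data are seen.

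**What to change.** Remove participant from the model terms in 9.8.4 and 9.8.5, and name one primary test in both the Abstract and 9.8.4. Either version works:

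- **Paired t-test.** Test the month-6 change with a two-sided paired t-test in the full analysis set, using participants with both scores. Keep the indication + baseline model as a supporting analysis.
- **Linear model.** Model the change on indication and baseline (rank 4, df 186 at 190). State how the overall mean is weighted across indications, and that the ordinary standard error is conditional on the observed baselines. If a population mean change is intended, say so and do not rely on that standard error, which undercovers (about 94% and 90% at assumed R2 of 0.1 and 0.3).

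Apply the same choice to every cross-indication change and time point in 9.8.5, and settle whether the four other questionnaires are analysed at three visits or at month 6 only.

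In the Abstract, align the primary population with 9.8.2. Reconcile the secondary analyses that use the responder population, including the continuer versus non-continuer comparison, with 9.8.1.1 and 9.9.

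Make the change before the interim database lock. The cost is wording only, with no new data and no change to missing-data handling. The paired t-test option is slightly conservative if indication means differ: the standard error is 1.1% larger at an assumed 0.4 SD difference for psoriasis and 4.2% larger at 0.8 SD.

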9.8.5 Secondary Efficacy Analyses

The following secondary endpoints will be analysed and summarised using general linear models and paired t-tests. The analyses summarising the changes across all indications will include participant, baseline levels and indication as terms in the analyses. Those analyses analysing changes within indications will use paired t-tests. Mean changes will be summarised with 95% confidence intervals derived from these analyses.

- Change in total WHODAS score 2 and 4 months after the initiation of adalimumab across all indications
- Change in total WHODAS score 6 months after the initiation of adalimumab in each indication
- Changes in WPAI:GI, K10, Flourishing Scale, and Subject Vitality Scale scores at 2, 4 and 6 months after the initiation of adalimumab, across all indications

- Change in disease-specific scores (HAQ-DI, SIBDQ, DLQI) at 2, 4 and 6 months after the initiation of adalimumab, in each indication

The proportion of patients at 6 months who remain on adalimumab, having satisfied the requirements for application for renewal of subsidy by special authority as defined below for each indication will be summarised for all indications combined and separately. These proportions will be summarised with exact 95% confidence intervals.

- **Rheumatoid arthritis:** $\geq 50\%$ decrease in active joint count from baseline AND a clinically significant response to treatment in the opinion of the physician
- **Crohn's disease:** CDAI score reduction by 100 points or CDAI score ≤ 150
- **Psoriasis:** PASI score reduction of $\geq 75\%$; or in the case of a patient had severe chronic plaque psoriasis of the face, or palm of a hand or sole of a foot at the start of treatment, the patient has a reduction in the PASI symptom subscores for all 3 of erythema, thickness and scaling, to slight or better, OR $\geq 75\%$ reduction in affected skin area.

9.8.6 Safety Analyses

Adverse events occurring while participants are on adalimumab will be coded using CTCAE classification individually listed by indication groups. The incidences and percentages of individuals experiencing AEs and SAEs within each indication will be summarized by System Organ Class (SOC) with further summaries by severity and relatedness (causality) categories. Adverse events leading to discontinuation and concomitant medications will also be listed and summarised.

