9.0 Research Methods

9.1 Study Design

This is a Phase IV, parallel-group, observational, multicentre study designed to investigate the effectiveness of adalimumab on health and disability outcomes in New Zealand patients diagnosed with rheumatoid arthritis, Crohn's disease and psoriasis.

The decision to commence treatment with adalimumab is to be made by the patient and the physician before including the patient in this study and has to be clearly separated and independent of the decision to include the patient in the study.

Overall, a minimum of approximately 190 subjects with these three IMIDs are planned to be enrolled in the study at up to 15 sites. Approximately 80 subjects will be enrolled into each of 2 parallel study groups of patients diagnosed with rheumatoid arthritis or Crohn's disease. A minimum of 30 subjects with psoriasis will also be enrolled. All subjects will receive at least 3 months of treatment with adalimumab. AbbVie is not supplying adalimumab; adalimumab is to be used according to the approved adalimumab New Zealand Datasheet and is to be prescribed by the physician under usual and customary practice of physician prescription. Continuation of adalimumab will depend upon the patient meeting the disease-specific response criteria as determined by the investigator

between 3 and 6 months, which will allow continuing reimbursement of drug supply under “Special Authority”.

To assess health and disability outcomes, the WHODAS 2.0 score will be assessed at baseline, 2, 4 and 6 months after treatment initiation with adalimumab. Work productivity will be assessed at these time points using the WPAI:GH V2.0 (8). Psychological distress will be measured using the K10 scale (9). Subject happiness will also be measured, Flourishing Scale (10), Subject Vitality Scale (11). Disease-specific patient reported outcomes (PROs) that are more commonly used in clinical practice; Health Assessment Questionnaire–Disability Index (HAQ-DI) (12), Short Inflammatory Bowel Disease Questionnaire (SIBDQ) (13), Dermatology Life Quality Index (DLQI) (14) will also be assessed. Variations of these disease-specific indices were used in some of the pivotal Phase III studies for adalimumab.

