9.1.4 Adalimumab dosing

The participating Physician will provide the patient with a prescription for adalimumab, along with instructions for appropriate use. The date of first dose of adalimumab will be recorded in the CRF and should closely align with the Baseline visit, but not before completion of the PRO questionnaires.

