9.8.1.2 Observational Period

The observational period will be from participant enrolment to 6 months or until any participant stops study medication or withdraws from the study.

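### On-drug adverse event percentages need exposure time beside them, because time at risk ends at drug stop and stopping between months 3 and 6 is built into the design

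*Combined protocol and SAP*

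**What the plan says.** Section 9.8.6 sets the summary measure: "The incidences and percentages of individuals experiencing AEs and SAEs within each indication will be summarized by System Organ Class (SOC", with further breakdowns by severity and causality. It restricts the input to on-drug events: "Adverse events occurring while participants are on adalimumab will be coded using CTCAE classification". Section 9.8.1.1 gives the same restriction, "Safety outcomes will only be considered while the patient is on adalimumab", and fixes the denominator, since the safety population is "defined as all participants enrolled into the trial who started study medication". Section 9.8.1.2 sets the follow-up: "The observational period will be from participant enrolment to 6 months or until any participant stops study medication or withdraws from the study".

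On exposure, section 9.1 states that "All subjects will receive at least 3 months of treatment with adalimumab" and makes continuation after that depend on disease-specific response between 3 and 6 months. The criteria are joint count plus physician opinion in rheumatoid arthritis, CDAI in Crohn's disease, and PASI or its alternatives in psoriasis. Section 9.2.3 also allows withdrawal at any time. On dates, section 9.1.4 says "The date of first dose of adalimumab will be recorded in the CRF". No section states that the last-dose date is a CRF item, although the 30-day call in sections 9.2.2 and 9.2.3 is timed from it.

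Section 9.8 plans no summary of time on drug, person-time rate or time-to-event estimate for safety. It leaves the term *incidences* undefined; next to *of individuals* it most naturally means counts, but a rate is not strictly excluded.

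**The concern.** Each patient contributes to the denominator in full, however short the time at risk. A patient who fails renewal at month 3 without an event counts as event-free just like one observed for 6 months. The percentage therefore mixes how often events occur with how long patients stay on drug.

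The unequal exposure comes from the plan's own renewal rule, and the rule differs by disease. Safety tables are laid out by indication, so a reader will naturally look across the columns. Without exposure beside them, that reader cannot tell a lower event rate from shorter treatment, and may take each figure as a 6-month risk.

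**Working it through.** **No plan figure to reproduce.** The documents give no event rate, stopping rate or safety precision target. Everything numerical below is an assumption shown over a range, except the group sizes in section 9.6 (about 80, about 80, at least 30) and the 3- and 6-month marks in section 9.1.

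**Model.** Let F(t) be the probability of a first event by month t on drug, and q the share who stop at month s, independently of event risk. Then

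- risk under full 6-month exposure: R = F(6)
- expected crude percentage: (1 − q)·F(6) + q·F(s)
- relative shortfall: q·(1 − F(s)/F(6))

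**Constant hazard h per month, s = 3.** F(t) = 1 − exp(−ht).

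- h = 0.01 (serious-event-like): F(6) = 5.82%, F(3) = 2.96%, so 1 − F(3)/F(6) = 0.49
- h = 0.10 (common-event-like): F(6) = 45.1%, F(3) = 25.9%, so 1 − F(3)/F(6) = 0.43

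| Share stopping | h = 0.01: crude % (true 5.82) | shortfall | h = 0.10: crude % (true 45.1) | shortfall |
|---|---|---|---|---|
| 10% | 5.54 | 4.9% | 43.2 | 4.3% |
| 30% | 4.96 | 14.8% | 39.4 | 12.8% |
| 40% | 4.68 | 19.7% | 37.4 | 17.0% |

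With constant or falling hazard and at least 3 months on drug, F(3) is at least half of F(6). The relative shortfall therefore cannot exceed q/2.

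**Sensitivity to timing and hazard shape.**

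- Stopping at month 4.5, q = 40%: the shortfall falls to 9.8% (h = 0.01) and 7.9% (h = 0.10).
- Front-loaded hazard, F(t) = 1 − exp(−H·(t/6)^0.5) with H = −ln(1 − R), R = 30%, q = 40%, s = 3: crude 26.9%, against 24.5% under constant hazard.
- Stopping at month 1, which withdrawal at any time permits despite the 3-month statement, R = 30%, q = 40%, constant hazard: crude 20.3%.

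**Does more stopping always mean more understatement?** Constant hazard:

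- R = 10%, 40% stop at month 3: crude 8.05%, loss 1.95 points (19.5% relative). R = 50%, 20% stop at month 3: crude 45.86%, loss 4.14 points (8.3% relative). The order reverses in points, though not in relative terms.
- R = 30% in both, 40% stop at month 5: loss 1.71 points; 25% stop at month 3: loss 3.42 points. The order reverses on either scale.

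**Does exposure adjustment recover R?** In 1,500 simulated trials with 80 patients, R = 30%, q = 40%, s = 3 and constant hazard, the crude percentage averaged 24.3%. One minus Kaplan-Meier averaged 29.6%, and the person-time rate converted to a 6-month risk averaged 29.7%.

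**Scale against chance.** With h = 0.01 and q = 30%, the gap is 80 × (0.0582 − 0.0496) = 0.7 patients in 80, and the sampling SD is √(0.058 × 0.942/80) = 2.6 points. At R = 30% the sampling SD of the crude percentage is about 5 points with 80 patients and 8 with 30.

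**The case against.** The strongest reply is that nothing is miscalculated. The plan never names the 6-month risk under full exposure as its safety target. It reports how many of those who started had an event while on drug, and for that the percentage is correct. This stands: a reader might infer that the plan understates its own safety quantity, and the documents do not support that.

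A reader might also infer that the understatement is largest in the indication with the most early stopping. That needs similar hazards and similar stop timing across diseases; the documents state neither, and the examples above reverse the order. Nor does the plan test or contrast safety between indications, so any comparison would be the reader's own.

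Persistence is also partly visible already. Section 9.8.5 reports the proportion still on adalimumab with renewal criteria met, by indication, and section 9.8.1.1 requires a flow diagram that includes discontinuations. This helps but does not give time on drug: the proportion is a single 6-month figure that counts a missing assessment as failure, and a flow diagram need not show when patients stopped. An event that itself causes stopping begins on drug and is counted, so it is not lost.

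Finally, the gap is modest and can be smaller than sampling error. That is true. In this model, however, it is always downward, and more patients do not remove it.

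**Conclusion.** This is a worthwhile, inexpensive improvement to reporting; it does not correct a wrong calculation. The on-drug percentages are valid for what they literally measure. They fall below the full-exposure 6-month risk whenever event-free patients stop early, and they are not comparable across indications with different persistence.

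The actual size cannot be derived from the documents. With constant hazard, stopping at month 3 and stopping independent of event risk, the relative shortfall is about 4–5% at 10% stopping and 17–20% at 40%. Later stopping or a front-loaded hazard makes it smaller; stopping before month 3 makes it larger. For rare serious events it amounts to less than one patient in 80 in the 30%-stopping example.

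**What to change.** In section 9.8.6, keep the percentages and add, by indication:

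- patient-years on adalimumab, from first to last dose within the 6-month period;
- first-event rates per 100 patient-years for AEs, SAEs and AEs leading to discontinuation, with exact Poisson 95% confidence intervals. Each patient should contribute time up to the first such event or the end of on-drug time. Counting first events only avoids intervals that are too narrow because of repeat events in one patient;
- a definition of *incidences* that says which column is a count, which a percentage and which a rate.

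Add the last-dose date to the CRF as an explicit item; the first-dose date is already recorded.

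The cost is a few table columns and one date field, with no extra visit. The rates have limits that should be stated beside them. They assume a roughly constant hazard over 6 months and stopping unrelated to event risk; if non-responders differ in event risk, the rates are biased too. They will be imprecise in psoriasis, where 30 patients give at most 30 × 0.5 = 15 patient-years at the minimum enrolment. This is why the rates should sit beside the percentages and not replace them.
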